2.0 TRIAL OBJECTIVES

The purpose of this clinical investigation is to assess the safety and effectiveness of the EDWARDS INTUITY Valve System in subjects with aortic stenosis or stenosis-insufficiency requiring replacement of the native aortic valve in premarket and post market phases.

Safety was determined by comparing safety endpoints to the objective performance criteria (OPC) defined by ANNEX R, Section R2, Table R.1 of BS EN ISO 5840:2009 (Cardiovascular implants – Cardiac valve prostheses) and effectiveness was evaluated based on improvement in NYHA Class and hemodynamic parameters compared to baseline.

2.1 PRIMARY SAFETY ENDPOINTS

The primary safety endpoints consist of:

- All cause mortality
 - Trial valve-related mortality
- Thromboembolism
- Valve thrombosis (trial valve)
- All hemorrhage
 - Major hemorrhage
- All paravalvular leak (trial valve)
 - Major paravalvular leak (trial valve)
- Endocarditis (trial valve)
- Structural valve deterioration (trial valve)
- Non-Structural valve deterioration (trial valve)
- Valve Malposition
- Valve Migration/ embolization
- Valve Instability
- Valve Dislodgment
- Hemolysis
- Reoperation
 - Trial valve-related reoperation
- Explant
 - Trial valve explant
- Implant-related new or worsened cardiac conduction disturbance*
 - requiring permanent pacemaker implant
 - not requiring permanent pacemaker implant

*Defined as new or worsened first degree atrioventricular (AV) block, second degree AV block (Mobitz I or Mobitz II), third degree AV block, incomplete right bundle branch block, right bundle branch block, intraventricular conduction delay, left bundle branch block, left anterior fascicular block, or left posterior fascicular block.

2.2 EFFECTIVENESS ENDPOINTS

The following effectiveness endpoints for assessment are:

- Device technical success is defined as the successful delivery and deployment of the trial valve with maximum of two attempts and subject leaving the OR with valve in place
- Procedural success is defined as device technical success followed by the absence of adverse events resulting in device reoperation implant of permanent pacemaker (with baseline sinus rhythm and no other pre-existing conduction issues), or valve-related death within discharge or 10 days post index procedure, whichever comes first.
- Cross-clamp time
- Cardiopulmonary bypass time
- The length of time in the intensive care unit (ICU)
- New York Heart Association (NYHA) functional class compared to baseline
- Hemodynamic performance (mean gradient, peak gradient, effective orifice area [EOA], EOA index, performance index, cardiac output [CO], cardiac index, valvular regurgitation (including paravalvular leak) by echocardiography)

A comparison of all effectiveness data for the EDWARDS INTUTY valve were made to current state of the art prosthetic heart valve literature published in peer reviewed journals at the time of PMA submission.

2.3 OTHER OUTCOMES

The following outcomes for additional evaluation are:

- Change in Short Form 12 version 1 (SF-12v2) Quality of Life questionnaire from Baseline to 1 year
- Laboratory testing (White Blood Cell Count, Red Blood Cell Count, Hemoglobin, Hematocrit, Plasma-free Hemoglobin or haptoglobin or serum LDH, Platelet Count) at screening and at 3, 6, 12 months and annually thereafter from post implant

2.4 GOOD CLINICAL PRACTICES STATEMENT

This trial was conducted in compliance with all applicable U.S. Federal regulations pertaining to trial devices including but not limited to: 21 CFR Part 50, Part 54, Part 56, Part 812, Good Clinical Practice (GCP) standards, and Health and Insurance Portability and Accountability Act (HIPAA).

3.0 RISK/BENEFITS ANALYSIS

3.1 RISK

As with all prosthetic heart valves, serious complications, sometimes leading to death, may be associated with the use of tissue valves. In addition, complications due to individual patient reaction to an implanted device, or to physical or chemical changes in the components, particularly those of biological origin, may occur at varying intervals (hours or days) necessitating reoperation and replacement of the prosthetic device.

For a complete listing of anticipated adverse events in this trial, see section 7.4 of this document. All safety events will be reported throughout the entire trial. Investigators will be notified of any additional risks identified that could affect the health, safety or welfare of the trial subjects.

3.2 MINIMIZING SUBJECT RISK

All adverse event rates will be collected, reviewed and evaluated. Clinical outcomes for all trial subjects will be routinely monitored by the Sponsor during the course of the trial. An independent Clinical Events Committee (CEC) will review and adjudicate safety endpoint related events as outlined in the CEC charter.

3.3 BENEFITS

Information gained from the continued follow up of these subjects may be of benefit to other patients with the same medical condition in the future.

4.0 FOLLOW UP PLAN

4.1 TRIAL DESIGN

This is a multi-center, prospective, non-randomized, single-arm, clinical trial to assess the safety and effectiveness of the trial valve system in subjects with aortic stenosis or stenosis-insufficiency requiring primary replacement of the native aortic valve. Premarket analysis was performed when the total late-patient years reached 800 and the number of subjects completing the one year (or greater) follow-up reached and/or exceeds 300. Post-market, all active subjects will be followed until the last enrolled subject completes their 5-year follow up.

4.2 TRIAL DESCRIPTION

Continued follow-up evaluations will be conducted on all active enrolled TRANSFORM™ Trial subject until the last enrolled subject complete the 5-year follow up.

5.0 TRIAL POPULATION

The trial population consists of subjects enrolled in the TRANSFORM™ Trial.

5.1 INCLUSION CRITERIA

During the enrollment phase of the trial, the following Inclusion, Exclusion and Intra-operative Exclusion Criteria was required:

1. Male or female, age 18 years or older
2. Subject has aortic stenosis or stenosis-insufficiency of an aortic valve requiring a planned replacement as indicated in the preoperative evaluation
3. Subject is scheduled to undergo planned aortic valve replacement with or without concomitant coronary bypass surgery
4. Provide written informed consent
5. Geographically stable and agrees to attend follow-up assessments until all subjects have completed 5 years of follow up

5.2 EXCLUSION CRITERIA

Pre-operative Exclusion Criteria:

1. Subjects with pure aortic insufficiency
2. Subjects requiring emergency surgery
3. Previous aortic valve replacement
4. Had prior mitral, tricuspid or pulmonic valve surgery, which included implant of a bioprosthetic valve, mechanical valve, or annuloplasty ring that will remain *in situ*;
5. Subjects requiring multiple valve replacement/repair
6. Requires a surgical procedure outside of the cardiac area (e.g., vascular endarterectomy, vascular bypass, tumor removal)
7. Aneurysm of the aortic root and/or ascending aorta requiring surgical intervention
8. Active endocarditis/myocarditis or endocarditis/myocarditis within 3 months prior to the scheduled AVR surgery
9. Myocardial infarction (MI) within thirty (30) days prior to valve replacement surgery;
10. Renal insufficiency as determined by creatinine ≥ 2.5 mg/dL at Screening or end-stage renal disease requiring chronic dialysis
11. Hyperparathyroidism
12. MRI or CT-scan confirmed cerebrovascular accident (CVA), or transient ischemic attack (TIA) within 6 months (180 days) of the procedure
13. Presence of non-cardiac disease limiting life expectancy to less than 12 months;
14. Hypertrophic obstructive cardiomyopathy (HOCM)
15. Left ventricular ejection fraction $\leq 25\%$
16. Documented history of substance (drug or alcohol) abuse within the last 5 years
17. Echocardiographic evidence of an intracardiac mass, thrombus, or vegetation
18. Hemodynamic or respiratory instability requiring inotropic support, mechanical circulatory support, or mechanical ventilation within 30 days prior to the procedure
19. Pregnancy, lactation, or planning to become pregnant
20. Currently incarcerated or unable to give voluntary informed consent
21. Leukopenia (WBC $< 3.5 \times 10^3/\mu\text{L}$), or acute anemia (Hgb < 10.0 gm/dL or 6 mmol/L), or thrombocytopenia (platelet count $< 50 \times 10^3/\mu\text{L}$), or history of bleeding diathesis or coagulopathy

22. History of myxomatous disease/connective tissue disorders (e.g., Marfan's Syndrome)
23. Current or recent participation (within 6 weeks prior to surgery) in an investigational drug or device trial

Intra-operative Exclusion Criteria

24. Subjects with anatomic variances which contraindicate implant of the trial valve, such as:
 - a. anomalous coronary arteries
 - b. annular deformation or extensive calcification of the annulus or aortic root which cannot be removed
 - c. significant calcium on the anterior mitral leaflet
 - d. pronounced septal calcification
 - e. position of coronary ostia relative to Model 8300ACA/ACD valve that would result in obstruction of blood flow
25. Available devices are not suitably sized for the subject's annulus

6.0 TRIAL PROCEDURES

A trial scheme in tabular format is provided in xxxxxx.

6.1 INFORMED CONSENT

All trial subjects were consented appropriately prior to enrollment in the TRANSFORM™ Trial. If re-consenting is required, an Institutional Review Board's (IRB's) approved informed consent will be utilized.

Each subject shall be given ample time to read the ICF in its entirety and ask questions in order to make an informed decision. The subject must sign and date the trial site's IRB approved ICF. In addition, the Investigator, or designee, and any witnesses will sign and date the ICF, as indicated.

6.2 SUBJECT SCREENING

At the time of this protocol revision, all subjects were enrolled in the trial and followed through 1-year follow up. For a complete description of the Subject Screening, Surgical Procedure, Subject Enrollment, Implant Procedure, Post Procedure Follow-Up, Discharge, POD 36, and POD 105 visits, please refer to a previous version (Revision N) of the TRANSFORM™ Protocol.

6.2.1 POD 195 VISIT (-15/+45 DAYS)

This visit is only required if echocardiography at three months showed a PVL >mild as determined by the Echo Core Lab or an implant-related new or worsened cardiac conduction disturbance.

These subjects will return for follow-up between POD 180 to 240 and the following assessments will be performed:

| | |
|--------------------------------------------------------------|--------------------------------------------------------------------------------------------------------------------------------------------------------------------------------------------------------------------|
| Subject status | |
| Date of Follow-Up | |
| NYHA Classification | |
| Echocardiography (TTE) | Peak and mean pressure gradients, EOA, EOA index, performance index, cardiac output, cardiac index, valvular regurgitation (including paravalvular leak) |
| Electrocardiogram | 12-Lead ECG (Cardiac Rhythm) |
| Anticoagulant therapy/Concomitant cardiovascular medications | Anticoagulants/anti-platelets and other Concomitant cardiovascular medications |
| Coagulation profile | May include PTT or PT or INR if subject is on anticoagulant therapy only |
| Laboratory Testing | WBC, RBC, hemoglobin, hematocrit, platelets, plasma-free hemoglobin (a 2 nd lab draw for plasma free hemoglobin is required within 48 hours if the first draw is >40mg/dl) or haptoglobin or serum LDH |
| Vital signs | Blood pressure, heart rate, weight |
| Adverse events/Complications | If applicable |

6.2.2 POD 390 VISIT (- 25/+45 DAYS)

Subjects will return for follow-up between POD 365 to 435 and the following assessments will be performed:

| | |
|--------------------------------------------------------------|--------------------------------------------------------------------------------------------------------------------------------------------------------------------------------------------------------------------|
| Subject status | |
| Date of Follow-Up | |
| NYHA Classification | |
| Echocardiography (TTE) | Peak and mean pressure gradients, EOA, EOA index, performance index, cardiac output, cardiac index, valvular regurgitation (including paravalvular leak) |
| Electrocardiogram | 12-Lead ECG (Cardiac Rhythm) |
| Anticoagulant therapy/Concomitant cardiovascular medications | Anticoagulants/anti-platelets and other Concomitant cardiovascular medications |
| Coagulation profile | May include PTT or PT or INR if subject is on anticoagulant therapy only |
| Laboratory Testing | WBC, RBC, hemoglobin, hematocrit, platelets, plasma-free hemoglobin (a 2 nd lab draw for plasma free hemoglobin is required within 48 hours if the first draw is >40mg/dl) or haptoglobin or serum LDH |
| QOL Survey | SF-12v2 |
| Vital signs | Blood pressure, heart rate, weight |
| Adverse events/Complications | If applicable |

6.2.3 PO YEAR 2 THROUGH SUBSEQUENT ANNUAL VISITS

After the POD 390 visit, the subject will return for follow-up site annually -60/+60 days until the trial ends. The following assessments will be performed:

| | |
|--------------------------------------------------------------|--------------------------------------------------------------------------------------------------------------------------------------------------------------------------------------------------------------------|
| Subject status | |
| Date of Follow-Up | |
| NYHA Classification | |
| Echocardiography (TTE) | Peak and mean pressure gradients, EOA, EOA index, performance index, cardiac output, cardiac index, valvular regurgitation (including paravalvular leak) |
| Electrocardiogram | 12-Lead ECG (Cardiac Rhythm) |
| Anticoagulant therapy/Concomitant cardiovascular medications | Anticoagulants/anti-platelets and other Concomitant cardiovascular medications |
| Coagulation profile | May include PTT or PT or INR if subject is on anticoagulant therapy only |
| Laboratory Testing | WBC, RBC, hemoglobin, hematocrit, platelets, plasma-free hemoglobin (a 2 nd lab draw for plasma free hemoglobin is required within 48 hours if the first draw is >40mg/dl) or haptoglobin or serum LDH |
| Vital signs | Blood pressure, heart rate, weight |
| Adverse events/Complications | If applicable |

At each postoperative assessment, the Investigator will determine the subject's availability for future follow-up visits. If any subject is seen at a time in addition to regularly scheduled follow-up visits, the visit will be recorded as an interim visit. The procedures performed at an unscheduled visit will be at the Investigator's discretion. Available data obtained at an unscheduled visit will be transcribed onto an Unscheduled Visit CRF.

6.2.4 VISIT WINDOWS

Visits must be scheduled for specific times before and after the date of the index procedure. It is important that this schedule is maintained for all subjects. To facilitate compliance, each visit has a visit window as described in Table 1 below. Visits not completed within these windows will be considered “done out of window.” Additional visits completed will be considered unscheduled visits. Trial visits should be scheduled as close to the early part of the visit window as possible so that if it is necessary to cancel and reschedule the visit, the visit may still be conducted within the required visit window.

Table 1: Follow-up Visit Days & Visit Windows

| Visit | Visit Window (Days) | Timing from Implant (Day 0) |
|-----------|---------------------|-----------------------------|
| POD 195* | - 15/+45 | Day 180 to Day 240 |
| POD 390 | - 25/+45 | Day 365 to Day 435 |
| PO Year 2 | - 60/+60 | Day 670 - 790 |
| PO Year 3 | - 60/+60 | Day 1035 - 1155 |
| PO Year 4 | - 60/+60 | Day 1400 - 1520 |
| PO Year 5 | - 60/+60 | Day 1765 - 1885 |

* Required for subjects with PVL >mild on POD 105 echocardiography as determined by the Echo Core Lab or an implant-related new or worsened cardiac conduction disturbance.

6.3 SUBJECT WITHDRAWAL

Subjects may voluntarily withdraw consent at any time during the clinical trial without jeopardizing their medical care. In addition, the Investigator, the IRB and or Edwards Lifesciences has the right to withdraw subjects from the trial for the following reasons: when continuation may jeopardize the health of the subject, protocol violations, adverse events or concurrent conditions, administrative or other reasons.

Subjects who withdraw from the trial for any reason will not be replaced

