6.4 SUBJECT REMOVAL FROM CLINICAL TRIAL

Although all subjects are informed of their right to withdraw from the clinical trial at any time, it is anticipated that such withdrawals will be infrequent. All measures should be taken by the Investigator and his/her staff to encourage subjects to return for required follow-up visits. The clinical trial objectives may be jeopardized if large numbers of subjects are lost to follow-up.

All subjects are expected to continue in the trial until the Sponsor notifies the Investigator in writing that further follow-up is no longer required, except in the event of death or upon the subject's written request for early withdrawal from the clinical trial. A copy of such requests will be kept with the source documentation.

A subject will be considered "*lost to follow-up*" and terminated from the trial when all of the following criteria are met:

- Failure to complete two consecutive visits without due cause
- Documentation of three unsuccessful attempts on three different dates over a period of at least 1 month by the Investigator or designee to contact the subject or next of kin.

All subjects who receive a commercial (a non-trial) heart valve and any subjects who have the EDWARDS INTUITY heart valve explanted will be followed through the end of the trial. Subjects previously exited from the trial due to receiving a commercial valve (at any time point) will be contacted and a request will be made to have them re-consented and reenrolled in the trial and followed through the end of the trial.

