6.5 TRIAL TERMINATION

If the Sponsor and/or the Principal Investigator should discover conditions arising during the trial that indicate that the trial should be terminated prematurely, an appropriate schedule for termination will be instituted. All trial subjects enrolled at the time the trial is terminated, will be followed by the Clinical Investigator for a period of five (5) years from the date of enrollment.

The trial plan includes continued annual follow-up until 5 years of follow up are completed on all subjects enrolled in the clinical trial.

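### Section 6.3 lets the investigator, IRB or sponsor withdraw a subject for an adverse event, an exit that 6.4 does not list, and no text requires vital-status or endpoint follow-up afterwards

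*Combined protocol and SAP*

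**What the plan says.** Section 6.3 first gives subjects the right to withdraw consent, then adds that "the Investigator, the IRB and or Edwards Lifesciences has the right to withdraw subjects from the trial for the following reasons". The list of grounds that comes next is broad: "when continuation may jeopardize the health of the subject, protocol violations, adverse events or concurrent conditions, administrative or other reasons".

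Section 6.4 starts from the opposite side: "All subjects are expected to continue in the trial until the Sponsor notifies the Investigator in writing that further follow-up is no longer required". Two exceptions are attached to that sentence: "except in the event of death or upon the subject's written request for early withdrawal from the clinical trial". The section then adds one further exit. A subject counts as lost to follow-up and is "terminated from the trial when all of the following criteria are met", the criteria being two consecutive missed visits and three documented failed contacts. It also protects two groups: recipients of a commercial valve, and "any subjects who have the EDWARDS INTUITY heart valve explanted will be followed through the end of the trial".

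Section 6.5 sets the goal: "The trial plan includes continued annual follow-up until 5 years of follow up are completed on all subjects enrolled in the clinical trial". Section 4.2 is narrower, since it commits to follow-up only of active subjects ("Continued follow-up evaluations will be conducted on all active enrolled").

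On analysis, 9.1.2.1 bases the primary late safety results on linearized rates that allow several events per patient, with Kaplan-Meier time to first event as an addition. Section 7.6 counts an unresolved complication once. Section 9.1.5 on missing data speaks only of effectiveness endpoints. The summary of non-completers in 9.2 names loss to follow-up, explant and death.

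**The concern.** The grounds in 6.3 read like those of a trial with a treatment to stop. Here the valve is in place and withdrawal stops only the observation. Adverse events are what this phase counts, so making one a ground for ending observation ties censoring to the outcome.

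Take a subject with a disabling stroke, or with endocarditis that does not lead to explant. Under 6.3 the site may take that subject off the trial. Under 6.4 the subject is expected to stay. If the site uses 6.3, later deaths, reoperations and recurrent events go unrecorded, and the planned tables would not show why the follow-up stopped.

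Section 6.4 recognises the same problem in one setting: it asks that subjects who had exited because they received a commercial valve be re-consented and followed to the end. Subjects withdrawn after other events have no such provision.

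**Working it through.** **Step 1. Set the texts side by side.**

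| Question | 6.3 | 6.4 |
|---|---|---|
| Who can end participation? | Subject, investigator, IRB, sponsor | Subject in writing; the sponsor by notice that follow-up is no longer required; the lost-to-follow-up rule |
| Is an adverse event a ground? | Yes | Not listed |
| Is an administrative reason a ground? | Yes | Not listed |
| Follow-up after exit? | None stated | To trial end for explanted and commercial-valve subjects only |

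Section 7.0 asks the investigator to follow an adverse event until it settles. That covers the event itself and not a later death or a different endpoint. The documents contain no other provision for follow-up after a 6.3 withdrawal.

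**Step 2. Effect on mortality (illustration).** The documents give no count of 6.3 withdrawals and no post-event hazard, so every input here is an assumption: death hazard h = 0.025 per year before an event, first-event hazard λ = 0.03 per year, death hazard b = k·h after the event with k = 2 or 4, a proportion q withdrawn at the event, and T = 5 years from the start of follow-up.

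- Patient-years before the event, per subject: A = (1 − e^(−aT))/a with a = h + λ = 0.055, so A = 4.371.
- Patient-years after the event with full follow-up: B = ∫₀ᵀ λ(e^(−bt) − e^(−at))/(a − b) dt, so B = 0.315 for k = 2 and 0.291 for k = 4.
- Observed linearized death rate = [hA + b(1 − q)B] / [A + (1 − q)B].

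| k | q | Deaths / patient-years per subject | Rate per 100 | Shortfall |
|---|---|---|---|---|
| 2 | 0 | 0.12506 / 4.6868 | 2.668 | – |
| 2 | 10% | 0.12348 / 4.6553 | 2.652 | 0.016 |
| 4 | 0 | 0.13840 / 4.6626 | 2.968 | – |
| 4 | 25% | 0.13112 / 4.5898 | 2.857 | 0.111 |
| 4 | 50% | 0.12384 / 4.5170 | 2.742 | 0.226 |

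Kaplan-Meier 5-year mortality for k = 4, with withdrawals censored, is 13.84% at q = 0, 13.35% at 25% and 12.85% at 50%. The expected number with a first event is 934 × λA = 934 × 0.131 ≈ 122, so q = 10%, 25% and 50% mean about 12, 31 and 61 withdrawals.

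**Step 3. Effect on the endpoint that triggers withdrawal.** Suppose the event is counted once, as 7.6 prescribes for an unresolved complication, and ignore death.

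- Probability of the event: 1 − e^(−0.15) = 0.1393.
- Patient-years before it: 0.1393/0.03 = 4.643. After it: 5 − 4.643 = 0.357.
- Rate = 0.1393 / [4.643 + (1 − q) × 0.357], which is 2.79 per 100 at q = 0, 2.84 at 25% and 2.89 at 50%.

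The event is already in the numerator and only time is lost, so this rate goes up. The time-to-first-event curve for that endpoint does not change, because the subject has already left its risk set.

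**The case against.** The strongest reply is that the two sections can be read together. Section 6.3 reserves a right and directs nobody to use it. Section 6.4 says subjects are expected to continue, which is softer than a prohibition and may be addressed to the subject's side. The word active in 4.2 already leaves out withdrawn subjects. This weakens any claim of flat contradiction. It does not close the gap, because on either reading nothing is collected after a 6.3 withdrawal.

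Three stronger readings are tempting, and the documents do not support them.

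- A reader might infer that 6.4 allows exit only for death or written request. It also terminates subjects who are lost to follow-up.
- A reader might infer that follow-up can end in the highest-risk subjects generally. Explanted and commercial-valve subjects are kept to trial end, which covers endocarditis leading to explant, and 7.0 keeps the event itself under review. The gap concerns other adverse events and what follows them.
- A reader might infer that all late rates and curves are biased in the valve's favour. Step 3 shows the opposite direction for a once-counted triggering event, and Step 2 depends on k being above 1.

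Nor does the rule in 9.1.5 against imputation make matters worse. It covers effectiveness tests only; safety has no missing-data rule at all.

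Finally, the documents record no 6.3 withdrawal for an adverse event. That objection stands, and it limits what can be said about size.

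**Conclusion.** The point holds in this form: 6.3 permits an exit that 6.4 does not list, no follow-up for vital status or endpoints is required after it, and 9.2 would not display it. Withdrawal after an adverse event would then be informative censoring. If later risk is raised, estimates for death, other endpoints and recurrences are too low. For the triggering endpoint, the linearized rate can be too high and the first-event curve is unaffected.

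The size is unknown and probably small. With post-event hazard doubled to quadrupled and 10% to 50% withdrawn at the event, the mortality rate is understated by about 0.02 to 0.23 per 100 patient-years. At the upper end of that range 5-year mortality falls by about one percentage point, and that would take some 61 withdrawals among 934 subjects. The change is worth making because it is cheap and because data not collected after exit may be hard to recover.

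**What to change.** Reconcile 6.3 with 6.4 for the follow-up phase. State that withdrawal by the investigator, the IRB or the sponsor ends study visits and procedures only, and that vital status and primary safety endpoint events continue to be collected by phone or from records to trial end unless the subject withdraws consent. The grounds in 6.3 need not be deleted.

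Add withdrawals, by initiator and reason, to the non-completion summary in 9.2. Identify any subject already withdrawn after an adverse event, so that the possible effect can be judged from real counts.

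Cost: a wording change with a short note to sites, a few phone or records contacts for subjects who would otherwise have left, and one table row.
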